4.2. Patient Selection

4.2.1. Inclusion Criteria

Patients are eligible to be included in the study only if all the following criteria apply at both the screening and baseline visits:

- 1. Capable of giving signed informed consent, which includes compliance with the requirements and restrictions listed in the Informed Consent Form (ICF) and in the protocol.
- 2. Male and female patients aged at least 18 years at the time of signing the ICF.
- 3. Body weight of greater than 40 kg at the time of signing the ICF.
- 4. Diagnosis of AD for a minimum of 1 year (before the Screening visit) using the Hanifin and Rajka criteria.
- 5. Moderate to severe AD (affected BSA of at least 10%, IGA-AD grade of at least 3, and EASI score of at least 16) at the screening and baseline visits.
- 6. Candidate for systemic treatment or phototherapy for AD.
- 7. Patients having a documented history of inadequate response to treatment with topical medications given for at least 4 weeks (at least 2 weeks for high potency topical corticosteroids), or as labeled, or for whom topical treatments are otherwise medically inadvisable.

8. Women of childbearing potential (WOCBP) must have a negative serum pregnancy test result at the Screening visit and a negative urine pregnancy test result at the Baseline visit. In addition, sexually active WOCBP must agree to use a highly effective method of contraception throughout the study and until at least 4 weeks after the end of study treatment. Highly effective methods of contraception are those that have a failure rate of less than 1% per year (when implemented consistently and correctly and when applicable, in accordance with the product label) and include hormonal contraceptives (combined oral contraceptive, patch, vaginal ring, injectable, or implantable); progestogen-only hormonal contraception associated with inhibition of ovulation (administration may be oral, injectable, or implantable); intrauterine devices or systems; self or partner vasectomy; or bilateral tubal ligation. Patients must have been on a stable dose of hormonal contraceptives for at least 4 weeks before the Baseline visit. Abstinence from heterosexual intercourse is an accepted method of contraception if it is the patient's lifestyle and is practiced for the duration of the study. Note: A woman of nonchildbearing potential is defined as a woman with surgical sterilization (hysterectomy, bilateral oophorectomy, or bilateral salpingectomy) or a woman in a postmenopausal status, defined as cessation of menses for at least 12 consecutive months without an alternative medical cause and a confirmatory folliclestimulating hormone test result or as cessation of menses for at least 24 consecutive months without an alternative medical cause.

4.2.2. Exclusion Criteria

Individuals meeting any of the following criteria at screening or baseline are ineligible to participate in this study:

- Therapy-resistant AD, defined as ≥2 treatment failures due to inadequate efficacy within the past 2 years of any biologic therapy, JAK inhibitor treatment or phototherapy administered at an adequate dose and duration according to the label or local/national guidelines. (Patients who stopped systemic treatment for reasons not related to lack of efficacy are not excluded).
- 2. Unstable AD with acute deterioration, requiring rescue therapy for AD within 4 weeks of the Screening visit or expected to require rescue therapy within 2 weeks after randomization.
- 3. History of allergy or hypersensitivity to any component of the study treatment.
- 4. Currently have active forms of other inflammatory skin disease or have evidence of skin conditions (eg, psoriasis, seborrheic dermatitis, lupus) at the Baseline visit that would interfere with evaluation of AD or response to treatment.
- 5. Active infection (eg, bacterial, viral, fungal) requiring treatment with systemic antibiotics within 4 weeks of the Screening visit.
- 6. Malignancy or history of malignancy except for treated (ie, cured) basal cell skin carcinoma.
- 7. Any chronic or recurrent medical condition associated with serious GI diseases, such as inflammatory bowel disease.
- 8. Any medical or psychiatric condition (eg, current major depression with a score for depressive symptoms ≥15 of HADS at baseline, schizophrenia, suicidal behavior, psychiatric hospitalization within the prior year) that, in the Investigator's opinion, would preclude the patient from adhering to the protocol, completing the study per-protocol, and/or would place the patient at unacceptable risk while receiving the investigational therapy.
- 9. Individuals with severe or uncontrolled asthma or any other concomitant condition that is likely to require systemic corticosteroid bursts during the study.
- 10. Any therapies and systemic treatments as described in protocol Table 3 "Nonallowed therapies and treatments" that do not comply with the indicated washout interval.
- 11. Any previous treatment with orismilast or failure of treatment for AD with apremilast or any other systemic PDE4 inhibitor.

- 12. Any condition, including laboratory or ECG abnormalities, that places the patient at unacceptable risk to participate in the study or confounds the ability to interpret data from the study.
- 13. Severe hepatic impairment based upon medical history and laboratory abnormalities (eg, low albumin and abnormal bilirubin levels).
- 14. Any of the following abnormalities in clinical laboratory test results at Screening, as assessed by the study-specific laboratory and confirmed by a single repeat test, if deemed necessary:
 - a) Absolute neutrophil count of less than 3.0×10^{9} /L (less than 3000/mm³).
 - b) Hemoglobin of less than 10.0 g/dL or hematocrit less than 30%.
 - c) Platelet count of less than 100,000 mm³.
 - d) Absolute lymphocyte count of less than 1.0×10^{9} /L (less than 1000/mm³).
 - e) Total bilirubin greater than 1.5 × the upper limit of normal (ULN); patients with a history of Gilbert's syndrome may have direct bilirubin measured and would be eligible for this study provided the direct bilirubin result is less than or equal to the ULN.
 - f) Alanine aminotransferase or aspartate aminotransferase greater than 2.5 × the ULN.
 - g) Serum creatinine greater than or equal to 1.5 mg/dL. For patients with a value of greater than or equal to 1.5 mg/dL, if their creatinine clearance is at least 60 mL/min (calculated using the Chronic Kidney Disease Epidemiology Collaboration creatinine equation), enrollment may be allowed.
- 15. History or evidence of hepatitis B virus infection at Screening. Patients with a positive hepatitis B surface antigen result are excluded. For patients with an isolated positive antihepatitis B core antibody result, the hepatitis B surface antibody result must also be positive to be eligible for this study.
- 16. History or positive test result for hepatitis C virus (HCV) antibody, indicating ongoing infection, at Screening. Confirmatory testing for HCV RNA will be conducted for patients who have a positive test result. Patients who have a negative result for HCV RNA will be eligible to participate in the study.
- 17. History of positive HIV test result or congenital or acquired immunodeficiency (eg, common variable immunodeficiency disease). Patients who are positive for HIV antibodies (HIV-1 or HIV-2) at Screening are excluded from the study.
- 18. Suicidal ideation or behavior in the past 12 months as indicated by a positive response (yes) to question 4 or 5 on the C-SSRS completed at the Screening visit or at Baseline.
- 19. Pregnant or breastfeeding.
- 20. History of alcohol or substance abuse within 6 months before Baseline that, in the opinion of the Investigator, will preclude participation in the study.
- 21. Institutionalized by court order or by local authority.
- 22. Regular use (more than 2 visits per week) of a tanning booth/parlor.

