- 13. Severe hepatic impairment based upon medical history and laboratory abnormalities (eg, low albumin and abnormal bilirubin levels)

- 14. Any of the following abnormalities in clinical laboratory test results at Screening, as assessed by the study-specific laboratory and confirmed by a single repeat test, if deemed necessary:
  - Absolute neutrophil count of less than the lower normal range of the Central Laboratory (LNR) i.e. 1.7 x 10^9/L (1700/mm^3)
  - Hemoglobin of less than 10.0 g/dL or hematocrit less than 30%
  - Platelet count of less than 100,000 mm^3
  - Absolute lymphocyte count of less than the lower normal range of the Central Laboratory (LNR) i.e. 0,9 x 10^9/L (900/mm^3)
  - Total bilirubin greater than 1.5 × the upper limit of normal (ULN); patients with a history of Gilbert's syndrome may have direct bilirubin measured and would be eligible for this study provided the direct bilirubin result is less than or equal to the ULN
  - Alanine aminotransferase or aspartate aminotransferase greater than  $2.5 \times$  the ULN
  - Serum creatinine greater than or equal to 1.5 mg/dL. For patients with a value of greater than or equal to 1.5 mg/dL, if their creatinine clearance is at least 60 mL/min (calculated using the Chronic Kidney Disease Epidemiology Collaboration creatinine equation), enrollment may be allowed.
- 15. History or evidence of hepatitis B virus infection at Screening. Patients with a positive hepatitis B surface antigen result are excluded. For patients with an isolated positive antihepatitis B core antibody result, the hepatitis B surface antibody result must also be positive to be eligible for this study.
- 16. History or positive test result for hepatitis C virus (HCV) antibody, indicating ongoing infection, at Screening. Confirmatory testing for HCV RNA will be conducted for patients who have a positive test result. Patients who have a negative result for HCV RNA will be eligible to participate in the study.
- 17. History of positive HIV test result or congenital or acquired immunodeficiency (eg, common variable immunodeficiency disease). Patients who are positive for HIV antibodies (HIV-1 or HIV-2) at Screening are excluded from the study.
- 18. Suicidal ideation or behavior in the past 12 months as indicated by a positive response (yes) to question 4 or 5 on the C-SSRS completed at the Screening visit or at Baseline
- 19. Pregnant or breastfeeding

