  - o The analysis of secondary efficacy endpoints was revised for consistency and to allow for comparison of ITT analysis results between the primary endpoint and continuous secondary efficacy endpoints. The sentence "For the continuous secondary efficacy endpoints (peak pruritus NRS, BSA, PGIS, PGIC, sleep disturbance NRS, skin pain NRS, DLQI, and POEM examination), an analysis of covariance, with treatment and disease severity as factors and Baseline value as covariate, will be applied. The mixed model for repeated measures may be used as a supportive analysis if appropriate." was changed to "For the continuous secondary efficacy endpoints (peak pruritus NRS, BSA, PGIS, PGIC, sleep disturbance NRS, skin pain NRS, DLQI, and POEM examination), a mixed model

for repeated measures will be performed similar to the supportive MMRM for the primary endpoint.

- PK analysis was revised from "trough" to "plasma".
- Appendix 3 was modified as follows:
  - The definition for Status of "Almost clear" / Score=1 was revised from "Trace faint pink erythema, with barely perceptible induration/papulation and no oozing/crusting" to "Trace faint pink erythema, no induration/papulation and no oozing/crusting".
  - As a result of the above change to the wording of the scale, the word "Validated" was removed from the title of the scale throughout.

Protocol version 2.0 dated 05 May 2022 was amended to create Protocol Amendment 2 (Protocol version 3.0) dated 14 April 2023; the amended version of the protocol supersedes version 2.0. The purpose of this amendment was to update the protocol per notification letter dated 09-FEB-2023 for adjustment of laboratory ranges in exclusion criterion No. 14, the update of the Investigators Brochure for orismilast version 15, dated 05. April 2023 and learnings from the recently completed clinical phase 2b trial, UNI50001-203, with orismilast in patients with moderate to severe psoriasis.

- General safety information regarding the use of orismilast is updated with the overall results from the UNI50001-203 trial in psoriasis patients, according to the updated Investigators Brochure version 15.
- The clinical risks and benefits of orismilast has been updated according to the recent learnings for the UNI50001-203 trial in patients with psoriasis and update of the Investigators Brochure version 15.

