- The exclusion criteria no. 14 on absolute neutrophil count and absolute lymphocyte count are by mistake not consistent with the reference range of the central laboratory and was corrected per notification letter dated 09. February 2023, as follows:
  - Absolute neutrophil count of less than 3.0x109 /L (less than 3000/mm3) was corrected to the lower normal range of the Central Laboratory (LNR) i.e. 1.7 x 109 /L (1700/mm3).
  - Absolute lymphocyte count of less than 1.0 x 109 /L (less than 1000/mm3) was corrected to the lower normal range of the Central Laboratory (LNR) i.e. 0,9 x 109 /L (900/mm3).
- The section regarding treatment discontinuation has been updated to more clearly state the requirement that if a patient experiences a TEAE assessed as Grade 3 or higher using the unique clinical descriptions of severity (Grade 2 or higher for the SOC of cardiac disorders) according to CTCAE version 5, the patient should be permanently discontinued from the study drug and not receive additional doses.
- Planned dosing schedule and adjustments has been described in more detail. This to help guide the Investigator in case of temporarily decreasing the dosage regimen if GI or other AEs considered probably or definitely related to the study drug are reported with a severity not compatible with maintaining the treatment as per-protocol.
  - A section for planned dosing schedule Titration over a maximum of 2 weeks has been created.

- A section describing the short dose reduction during the titration period has been updated.
- A section describing dose reductions and temporary treatment discontinuations after the titration period has been created.
- A section describing the examples of supportive treatment for side effects and medical treatment for tolerability issues that may arise during the treatment (e.g. metoclopramide for nausea/vomiting, loperamide for diarrhea, acetaminophen/paracetamol and NASID for headache) have been added.
- Safety blood samples for week 12 have been added in Table 4. Schedule of Assessments, to allow for closer monitoring of all safety laboratory assessments (hematology, serum chemistry, urinalysis) between weeks 8 and 16.
- The adverse events section has been updated with details to emphasize that all AEs must be graded by using the CTCAE grading system version 5.0, with reference to the unique clinical descriptions of severity for each AE in the guidance document.

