СМН	Cochran-Mantel-Haenszel
C-SSRS	Columbia-Suicide Severity Rating Scale
CTCAE	Common Terminology Criteria for Adverse Events
DLQI	Dermatology Life Quality Index
EASI	Eczema Area and Severity Index
EASI50	50% reduction in EASI
EASI75	75% reduction in EASI
EASI90	90% reduction in EASI
ECG	Electrocardiogram
eCRF	Electronic Case Report Form
HADS	Hospital Anxiety and Depression scale
HBcAb	Antihepatitis B core antibody
HBsAb	Hepatitis B surface antibody
HBsAg	Hepatitis B surface antigen
HBV	Hepatitis B Virus
HCV	Hepatitis C Virus

Abbreviation	Description
IB	Investigator's Brochure
ICF	Informed Consent Form
ICH	International Council for Harmonisation
IGA-AD	Investigator Global Assessment for AD
IRB	Institutional Review Board
ITT	Intent-To-Treat
IWRS	Interactive Web Response System
JAK	Janus kinase inhibitors
LS	Least squares
MAR	Missing At Random
Max	Maximum
MedDRA	Medical Dictionary for Regulatory Activities
Min	Minimum
MMRM	Mixed Model for Repeated Measures
N/A	Not Applicable
NCI	National Cancer Institute
NRS	Numeric Rating Scale
PCFB	Percentage Change from Baseline
PD	Pharmacodynamics
PDE	Phosphodiesterase
Pdf	Portable document format
PGIC	Patient Global Impression of Change
PGIS	Patient Global Impression of Severity
РК	Pharmacokinetic
POEM	Patient Oriented Eczema Measure
PP	Per Protocol
PRO	Patient-Reported Outcome
PT	Preferred Term
Q1	First quartile, 25th percentile of the data
Q3	Third quartile, 75th percentile of the data
QC	Quality Control

Abbreviation	Description
QoL	Quality of Life
QTc	Corrected QT Interval
REML	Restricted maximum likelihood
RNA	Ribonucleic acid
SAE	Serious Adverse Event
SAP	Statistical Analysis Plan
SAS	Statistical Analysis System
SD	Standard Deviation
SE	Standard Error
SI	Standard International System of Units
SoA	Schedule of Assessments
SOC	System Organ Class
SOP	Standard Operating Procedure
TEAE	Treatment-Emergent Adverse Event
TFL	Table, Figure and Listing
ULN	Upper Limit of Normal
US	United States
WHO	World Health Organization
WOCBP	Women of Childbearing Potential

2. Purpose

The purpose of this statistical analysis plan (SAP) is to ensure that the data listings, summary tables and figures which will be produced, and the statistical methodologies which will be used, are complete and appropriate to allow valid conclusions regarding the study objectives based on Protocol v2.0.

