6.5. Protocol Deviations

Protocol deviation management at Syneos Health is detailed in Protocol Deviation and Non-compliance Management (3101.W02). For details on the process for defining analysis datasets refer to (Blind) Data Review and Definition of Analysis Sets SOP (3911). The Protocol deviation criteria are graded as minor and major.

Patients with a major protocol deviation affecting efficacy analysis will be excluded from the PP population. The list of major protocol deviations potentially leading to PP population exclusion includes at least the following deviations:

- Violations of inclusion or exclusion criteria.
- Use of disallowed medication (that may influence the interpretation of efficacy results).
- Non-compliance with study medication intake: less than 80% of total number of tablets during entire treatment period or during the last 4 weeks.
- Major deviation from study specific instructions/procedures.

The final list of patients who are to be included in the PP population will be determined at the Blinded Data Review Meeting (BDRM). The BDRM will occur when all or nearly all queries have been resolved and the database is near to final. For the BDRM meeting, a BDRM Preparation Plan will be prepared. This plan will detail further the types of protocol deviation criteria and will include, as a minimum: 1) the exact criteria which will be used to determine if a patient will be excluded from the PP population; 2) the listings which will be prepared for sponsor review in order to determine which patients to exclude from the PP population. Details of patient specific exclusions from the PP population will be detailed in the BDRM Report.

7. General Aspects for Statistical Analysis

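### Could the outdated neutrophil and lymphocyte exclusion limits in the SAP turn eligible patients into eligibility violators?

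*SAP*

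**What the plan says.** SAP Section 2 (Purpose) describes the planned outputs as supporting "valid conclusions regarding the study objectives based on Protocol v2.0". The protocol supplied is v3.0 of 14 April 2023. On that amendment, its Appendix 15 says "the amended version of the protocol supersedes version 2.0".

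SAP Section 4.2.2, criterion 14, items a) and d), reads "Absolute neutrophil count of less than 3.0" and "Absolute lymphocyte count of less than 1.0" (both x 10^9/L). Protocol Section 7.2, criterion 14, reads "Absolute neutrophil count of less than the lower normal range of the Central Laboratory (LNR) i.e. 1.7 x 10" and "Absolute lymphocyte count of less than the lower normal range of the Central Laboratory (LNR) i.e. 0,9 x 10" (to the ninth, per litre). The protocol synopsis agrees with Section 7.2. Appendix 15 explains the change: the earlier limits were "by mistake not consistent with the reference range of the central laboratory", and they were corrected by a notification letter of 09 February 2023 and then in v3.0.

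On consequences, SAP Section 6.5 states: "The list of major protocol deviations potentially leading to PP population exclusion includes at least the following deviations". Breaches of the eligibility criteria head the list that follows. SAP Section 8.1 lists such breaches by patient, and Section 8.2 summarises deviations by treatment group.

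**The concern.** Two current documents give different numbers for the same eligibility criterion, and SAP Section 6.5 does not say which protocol version defines a violation. Read literally, a patient with screening neutrophils of 2.5 x 10^9/L who was enrolled properly under v3.0 meets an exclusion criterion in the SAP. That patient could appear in the listing of eligibility violations and in the deviation table, and might be removed from the per-protocol population. The per-protocol repeats of the primary and key secondary analyses would then omit patients who broke no rule.

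Two further points seem to strengthen the worry. Protocol Section 14 gives the SAP precedence where the two documents differ. And SAP Section 14, which records departures from the protocol, mentions only the added randomized population and the added EASI100 endpoint.

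**Working it through.** No sample size, power or error rate is at issue, so the check is a comparison of texts followed by tracing the path from the text to a result.

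**1. Size of the mismatch.**

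| Count (x 10^9/L) | SAP 4.2.2 excludes below | Protocol 7.2 excludes below | Band in dispute |
|---|---|---|---|
| Neutrophils | 3.0 | 1.7 | 3.0 - 1.7 = 1.3 (1300/mm3) |
| Lymphocytes | 1.0 | 0.9 | 1.0 - 0.9 = 0.1 (100/mm3) |

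Only patients inside a band, enrolled once the corrected limits applied at their site, can be eligible under the protocol and ineligible under the SAP's text. Neither document gives the distribution of these counts or enrolment by protocol version, so no number of patients can be computed. In both documents criterion 14 also allows a confirmatory repeat test, so one value does not always settle the matter.

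**2. What uses SAP Section 4.2.2.** It sits under the study design heading and restates the protocol. SAP Section 6.5 refers deviation handling to two standing procedures and leaves the exact per-protocol exclusion criteria to a preparation plan for the Blinded Data Review Meeting. Sections 8.1 and 8.2 report violations and deviations, and neither cites Section 4.2.2. Sites check eligibility at Screening and Baseline under protocol Table 4. A protocol deviation is a departure from the protocol, not from a summary of it in the SAP.

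**3. What must happen before a result changes.** All of the following are needed:

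- a patient falls in a band and was properly enrolled under the corrected limits;
- whoever classifies deviations works from the SAP summary instead of the protocol;
- the deviation is graded major;
- the blinded review decides that it bears on the efficacy analysis, as the per-protocol definition in SAP Section 6.4 requires.

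The documents do not suggest the second step would happen. Nor do they give a reason why a count at or above the central laboratory's lower limit would affect EASI.

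**4. What would change.** If only the first two steps occurred, a listing or deviation table would carry a wrong entry. If all four occurred, the per-protocol repeats would lose that patient. The ITT and safety populations are both built from randomized patients who took at least one dose (SAP Sections 6.2 and 6.3), with no eligibility condition. The primary analysis is on ITT (SAP Section 9.1).

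**5. The undeclared difference.** Appendix 15 records the earlier protocol limits as 3.0 and 1.0. Against v2.0, the version the SAP names, its criterion 14 matches, so SAP Section 14 had nothing to declare.

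**6. Whether an added rule would help.** An obvious rule is to judge violations by the protocol version in force at the site on enrolment. The letter is dated 09 February 2023 and v3.0 is dated 14 April 2023, which is 19 + 31 + 14 = 64 days later. The documents do not say when sites applied either one. If sites acted on the letter while v2.0 was formally in force, that rule would label correctly enrolled patients as violators. Replacing the numbers in the SAP without any rule could err the other way, by clearing in-band patients enrolled under the earlier limits.

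**The case for a change.** The best case for acting is that the remedy is cheap and the ambiguity is on paper. Eligibility breaches come first in the SAP's list of major deviations, no governing version is named, and the preparation plan that might settle it is not among the supplied documents, so it cannot be assumed to do so. If the SAP predates v3.0, that explains the text but does not bring it up to date.

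Part of this stands. The SAP's version reference and criterion 14 do not match the current protocol, and the passages need to be reconciled.

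The step from there to a changed analysis does not stand. The precedence clause in Protocol Section 14 introduces the SAP as giving further detail on analysis variables and methodology. It does not clearly extend to who was eligible to enrol. Choosing the applicable limits for each patient is ordinary work for the blinded review, which SAP Section 6.5 already requires to set exact criteria beforehand. That the plan cannot be seen here is not evidence that it is wrong.

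**Conclusion.** The discrepancy is genuine but clerical: a design summary carried over from a superseded protocol version. It does not call for a change to the plan. No analysis rule reads from the outdated text, the ITT and safety results cannot move, and an effect on the per-protocol repeats needs a chain of steps that the documents do not support. The number of patients concerned is unknown and may be zero.

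This rests on two assumptions. Deviations are recorded against the protocol limits that applied at the site, including the correction notified on 09 February 2023. The blinded review follows the process in SAP Section 6.5. The SAP's date is not visible, so it may have been correct when written. No view is taken on which laboratory limit is clinically appropriate. Aligning the two passages is document control and alters no planned analysis.
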